8.7.2 Training in diabetes and carbohydrate counting

During the run-in period all Subjects should have reinforced diabetes training including carbohydrate counting e.g. sessions with a diabetes educator, dietitian or qualified site staff (i.e. diabetes specialised nurse) according to local practice.

It is the Investigators responsibility to ensure that the Subject is adequately trained and has a satisfactory knowledge in:

- Recognition of carbohydrates in commonly eaten foods
- Ability to count the carbohydrate content in typical portions of simple foods
- Ability to interpret a nutrition label for carbohydrate content
- Glycaemic targets
- Preventing and treating hypoglycaemia using oral carbohydrates
- Ability to sum up the carbohydrate content of a meal

8.7.3 Training in trial product and pen handling

The Subjects should be trained in how to handle the insulin pen system when handed out the first time. The Subjects must demonstrate for the Investigator at the following visit after NovoPen Echo[®] and the pre-filled PDS290 pen-injector (FlexTouch[®]) has been handed out, that the Subject can use the pen correctly. Training should be repeated during the trial if necessary. It is important to emphasise that the Subject should remember the following:

- Always use a new needle for each injection as this will prevent contamination and blocked needles
- Priming to ensure the insulin flow
- The needle should be kept in the skin while counting slowly to 6 after the dose counter has returned to zero after injection. If the needle is removed too early then the full dose may not have been delivered

Important:

The Subjects should be thoroughly trained in distinguishing between the basal insulin and the bolus insulin. The pens will come in different colours and types, so they can be differentiated. The bolus insulins are to be injected with a durable pen (NovoPen Echo[®]) and should be loaded with a Penfill[®] before use. The basal insulin is to be injected with a pre-filled PDS290 pen-injector (FlexTouch[®]). The Subjects must be instructed to always check the name on the label before administering the insulin.

8.7.4 Safety precautions

The Investigator must instruct the Subjects always to carry the following supplies in case of hypoglycaemic episodes and need for ketone measurement (as described in section [8.5.1.1](#) and [8.5.1.2](#)):

- Glucagon for injection, according to local practice
- A fast-acting glucose preparation (e.g. tablets or powder)
- Urine sticks for ketone monitoring

The Subject must be trained in how and when to use the supplies.

8.8 Subject compliance

Throughout the trial, the Investigator will remind the Subjects to follow the trial procedures and requirements to ensure Subject compliance. If a Subject is found to be non-compliant, the Investigator will remind the Subject of the importance of following the instructions given including taking the trial products as prescribed.

Treatment compliance:

To ensure treatment compliance, the Investigator will at each visit assess the Subject's compliance by evaluating the glycaemic control, adherence to the visit schedule and completion of the Subject's diary including the SMPG profiles. If a Subject is being non-compliant with the treatment the Investigator must discuss this with the Subject and emphasise the importance of being in compliance.

9 Trial supplies

Trial supplies comprise trial products and auxiliary supplies. Additional details regarding trial supplies can be found in the Trial Materials Manual.

Trial products must not be dispensed to any person not included in the trial. Trial product must not be used, if it does not appear clear and colourless.

9.1 Trial products

The following trial products will be provided by Novo Nordisk A/S:

Table 9–1 Trial Products

Trial product	Strength	Dosage form	Route of administration
Faster aspart (blinded for the meal-time arm) ^a (IMP)^b	100 U/mL	Penfill® 3 mL	s.c.
Faster aspart (open-label for the post-meal arm) ^a (IMP)^b	100 U/mL	Penfill® 3 mL	s.c.
Insulin aspart (NovoRapid®) (blinded for the treatment period) (IMP)^b	100 U/mL	Penfill® 3 mL	s.c.
Insulin aspart (NovoRapid®) (open- label for the run-in period)	100 U/mL	Penfill® 3 mL	s.c.
Insulin degludec (open-label) (IMP)^b	100 U/mL	Pre-filled PDS290 pen-injector 3 mL	s.c.

^a Faster aspart is the short name for faster-acting insulin aspart and will be used as text on the labels.

^b Investigational medical product

All bolus insulins will be administered with NovoPen Echo®. Penfill® is the cartridge used for durable Novo Nordisk pens. Basal insulin will be administrated with a pre-filled PDS290 pen-injector (FlexTouch®).

9.2 Labelling

Labelling of the trial products will be in accordance with Annex 13⁴³, local regulations and trial requirements.

Labelling will include the product related requirements and precautions.

Each Investigator site will be supplied with sufficient trial products for the trial on an on-going basis controlled by the IV/WRS. Dispensing unit numbers (DUNs) will be distributed to the sites according to enrolment and randomisation.

The Investigator must document that direction for use is given to the Subject orally and in writing at each dispensing visit. Direction for use must as a minimum be provided to the Subject in writing at the first dispensing visit (Visit 2).

9.3 Storage

Table 9–2 Storage of trial products

Trial product	Storage conditions (not-in-use)	In-use conditions ^a	In-use time ^a
Faster aspart	Store in refrigerator (2°C – 8°C) Do not freeze Protect from light	Store below 30°C Do not refrigerate Do not freeze Protect from light	Use within 4 weeks
Insulin aspart (NovoRapid®)	Store in refrigerator (2°C – 8°C) Do not freeze Protect from light	Do not store above 30°C Can be stored in refrigerator (2°C – 8°C) Do not freeze Protect from light	Use within 8 weeks
Insulin degludec	Store in refrigerator (2°C – 8°C) Do not freeze Protect from light	Do not store above 30°C Can be stored in refrigerator (2°C – 8°C) Do not freeze Protect from light	Use within 8 weeks

^a In-use time starts when first dose is taken.

The Investigator must ensure the availability of proper storage conditions, and record and evaluate the temperature. The Investigator must inform Novo Nordisk **immediately** if any trial product has been stored outside specified conditions (e.g. outside temperature range).

For Japan only: The head of the trial site or the trial product storage manager if assigned by the head of the trial site must ensure the availability of proper storage conditions, record and evaluate the temperature.

Trial product that has been stored improperly must not be dispensed to any Subject and should be made temporarily unavailable in the IV/WRS and stored separately (quarantined) within the correct

temperature range until it has been evaluated and approved for further use by Novo Nordisk. The Investigator must take appropriate action to ensure correct storage.

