5.5 Rationale for treatment

Based on the currently available pharmacokinetic data on faster-acting insulin aspart it is anticipated that treatment with faster-acting insulin aspart as a meal-time insulin will enable insulin therapy to more closely mimic a physiologic insulin secretory pattern. Consequently, the PPG excursions may be more effectively controlled. For further details see the current version of the faster-acting insulin aspart IB^{[17](#)}.

NovoRapid® will be used as a comparator to faster-acting insulin aspart in order to compare the effect and safety of faster-acting insulin aspart to the currently marketed insulin aspart formulation. For further details see the current version of the NovoRapid® SmPC^{[15](#)} or the U.S. NovoLog® Label information^{[16](#)}. As this is a partly double-blind trial, NovoRapid® and faster-acting insulin aspart will be titrated following the same recommendations.

Insulin degludec has been chosen as the basal insulin because it is a once-daily basal insulin and as efficacy and safety has been studied in adult Subjects and recently in a paediatric population^{[19](#)}. The flat and stable glucose-lowering effect of insulin degludec makes it an optimal insulin when assessing the properties of bolus insulin (faster-acting insulin aspart compared to NovoRapid®). For further details see the current version of the Tresiba® EU SmPC^{[20](#)} and if not approved in the country of interest see the insulin degludec IB^{[22](#)}.

The treatment targets are aligned with the current ISPAD Clinical Practice Consensus Guidelines^{[7](#)}.

6 Trial population

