9.5 Auxiliary supplies

9.5.1 Auxiliaries supplied by Novo Nordisk A/S

The following auxiliaries will be supplied by Novo Nordisk A/S:

- NovoPen Echo®
- Direction for use
- BG meters, and ancillary for BG meters
- Needles, the size of the needle will be a maximum of 8 mm
- Standardised liquid meal (for the subgroup only)
- CGM supplies as described in [Appendix B](#) (for the subgroup only)
- Strips for ketone measurement
- A fast-acting glucose preparation (e.g. tablets or powder)

10 Interactive voice/web response system

A trial-specific IV/WRS will be set up which can be accessed at any time via the internet or telephone. Access to the IV/WRS must be restricted to and controlled by authorised persons.

IV/WRS is used for:

- Screening
- Screening failure
- Run-in failure
- Randomisation
- Medication arrival
- Run-in dispensing
- Dispensing
- Treatment discontinuation
- Completion
- Code break
- Drug accountability
- Data change

As the trial is blinded with regards to faster-acting insulin aspart and NovoRapid® it is important that, at all times during the trial, only DUNs allocated by the IV/WRS are dispensed to the Subject.

If a Subject requires additional trial product between dispensing visits, the site must perform an additional dispensing session in IV/WRS.

IV/WRS user manuals will be provided to each trial site.

11 Randomisation procedure and breaking of blinded codes

At randomisation (Visit 14) the Subject will be randomised to either faster-acting insulin aspart or NovoRapid®, both in combination with insulin degludec.

The randomisation will be carried out in a 1:1:1 manner to the three different treatment arms described below using the IV/WRS:

- Meal-time faster-acting insulin aspart and insulin degludec
- Meal-time NovoRapid® and insulin degludec
- Post-meal faster-acting insulin aspart and insulin degludec

The randomisation will be stratified according to age at randomisation (Visit 14):

- $1 \leq \text{age} < 3$
- $3 \leq \text{age} < 6$
- $6 \leq \text{age} < 12$
- $12 \leq \text{age} < 18$

The Investigators must strive to include Subjects in the youngest age groups (age < 6), to enable investigation of the efficacy and safety of faster-acting insulin aspart in these age groups. It will be attempted to include at least 20 Subjects below 6 years of age in each treatment arm.

The bolus insulin treatment is double blinded, except for the post-meal faster-acting insulin aspart treatment arm.

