2.12 Section 9.2 Labelling

....

The Investigator must document that direction for use is given to the Subject orally and in writing at ~~each the first dispensing visit (Visit 2). Direction for use must as a minimum be provided to the Subject in writing at the first dispensing visit (Visit 2).~~

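### Do the different in-use storage rules for the two blinded bolus insulins threaten the blind?

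*Protocol*

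**What the plan says.** Protocol section 9.3, Table 9-2, has one row for faster aspart, one for NovoRapid and one for insulin degludec. Before use, the two bolus products are stored alike. In use they differ. Faster aspart is under "Store below 30°C Do not refrigerate Do not freeze Protect from light", with four weeks from first dose. NovoRapid has the same 30°C ceiling in slightly different words, "Can be stored in refrigerator", and has eight weeks.

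Table 9-1 in section 9.1 separates blinded from open-label cartridges; Table 9-2 does not. Section 11 states: "The bolus insulin treatment is double blinded, except for the post-meal faster-acting insulin aspart treatment arm". The products compared under blinding are therefore meal-time faster aspart and meal-time NovoRapid.

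The protocol names two safeguards for the blind. Section 10 confines dispensing to unit numbers allocated by the IV/WRS. Section 5.5 sets a common titration rule: "As this is a partly double-blind trial, NovoRapid® and faster-acting insulin aspart will be titrated following the same recommendations". Neither mentions in-use handling or label wording. Section 9.2 places labelling under Annex 13, local regulations and trial requirements, and section 9 refers further supply details to a Trial Materials Manual, which is not among the documents supplied.

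**The concern.** Every subject reaches randomisation after 12 weeks on open-label NovoRapid. If the Table 9-2 rows were then applied product by product, a subject told to stop refrigerating the pen in use and to discard it sooner could infer faster aspart. If the run-in rule simply carried over, blinded faster aspart could be kept outside its stated limits, in that arm only.

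Three other places seem to add weight:

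- Footnote a to Table 9-1 says "Faster aspart is the short name for faster-acting insulin aspart and will be used as text on the labels".
- Section 8.7.3 says "The Subjects must be instructed to always check the name on the label before administering the insulin".
- Protocol Amendment 2 changes the section 9.2 sentence that begins "The Investigator must document that direction for use is given to the Subject orally and in writing at" so that it refers to the first dispensing visit, Visit 2, when the bolus insulin is still open-label.

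Steps 1 and 3 of the testing hierarchy compare the two blinded arms. Since HbA1c is measured centrally, inferred allocation would act mainly on self-reported hypoglycaemia, adverse event reporting and causality, and the investigator's discretion in titration.

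**Working it through.** The plan states no figure on this point, so there is none to reproduce. The check has two parts: the text, then the cartridge arithmetic.

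**1. Are the rows in conflict?** The NovoRapid row permits refrigeration but does not require it. The 30°C ceilings are effectively the same, and four weeks lies inside eight. Handling that meets the faster aspart row therefore also meets the NovoRapid row, so a single text can comply with both. If that text is tighter than the run-in rule, both blinded arms see the same change and it reveals nothing.

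**2. Could product-specific rules reach a blinded subject?** The site does not know the product, and section 11.1 allows the code to be broken only in a medical emergency. The site therefore cannot select a row. The only remaining route is label or leaflet text printed by the sponsor. No passage says that such text differs between the blinded cartridges.

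**3. Do the supporting passages show more?**

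- Footnote a is attached to both faster aspart rows, the open-label one included. It explains a short name and does not say what a blinded label reads.
- The label check in section 8.7.3 closes a paragraph on telling basal from bolus insulin. It concerns mix-ups, not allocation.
- No passage says that the direction for use contains storage rules. Section 9.5.1 lists it among the auxiliaries, directly after the pen used for all bolus insulins.

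**4. When would four versus eight weeks matter?** From Table 9-1, a cartridge holds 3 mL × 100 U/mL = 300 U.

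- Four-week limit: 300 / 28 = 10.7 U/day.
- Eight-week limit: 300 / 56 = 5.4 U/day.

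Below these rates the cartridge outlasts the limit. In Appendix A, Table 3-1, the largest total daily dose with bolus below 10.7 U is 20 U at 50:50 and 14 U at 30:70 (bolus 10 U in each; the next rows give 11 U). These are mainly young children.

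Two assumptions that the documents do not supply move the four-week threshold:

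| Assumption | Four-week threshold (bolus U/day) |
|---|---|
| No priming, one cartridge | 10.7 |
| 1 U priming × 3 injections | 10.7 − 3 = 7.7 |
| 2 U priming × 3 injections | 10.7 − 6 = 4.7 |
| Two cartridges in parallel, no priming | 600 / 28 = 21.4 |

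**5. Return of product.** Section 9.4 has subjects return part-used product at every dispensing visit. Taking week as visit number minus 14 (Visit 26 is week 12 and Visit 40 is week 26), the treatment-period site visits fall at weeks 0, 2, 4, 8, 12, 14, 17, 20, 24 and 26. The longest gap is 4 weeks. If most of these visits dispense, part-used cartridges go back at about the four-week point whatever the dose. The dispensing row of the flow chart is not legible in the text supplied, so this is an assumption. The thresholds in step 4 are thus upper bounds that ignore returns.

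**6. How many subjects?** The two blinded arms are planned at 2 × 250 = 500. That is the size of the arms, not the number exposed: a subject who keeps the pen in use out of the refrigerator meets no difference in storage conditions.

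**The case for a change.** The best case for a change is that the protocol applies exactly this reasoning elsewhere. It gives the blind as the reason for common titration recommendations, but states no equivalent for handling or labels. Section 9.2 also says labels carry product-related content, which, read beside Table 9-2, could mean different text on the two blinded cartridges. Section 9.3 requires immediate notice of product stored outside its conditions, and a blinded investigator could not tell from the table whether a refrigerated in-use cartridge qualifies. Return of product may blunt the time limit but does nothing about refrigeration. The remedy would be short.

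The textual part of this stands: a common in-use rule is not written in the protocol, the amendments or the SAP. The rest is weaker. Product-related content on labels is compatible with one shared text that respects both products. The notification duty in section 9.3 sits with rules on quarantine and on not dispensing affected stock, so it bears mainly on product held at the site, for which the two rows are identical. The refrigeration difference becomes visible only if the sponsor issues separate instructions within a blinded comparison, and no document shows that.

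**Conclusion.** The observation is correct, but it concerns unwritten supply detail and not a defect in the design or analysis. Table 9-2 reads as a list of product properties; nothing shows that it is the wording given to subjects. A sponsor preparing blinded cartridges under Annex 13 and its own trial requirements would ordinarily put one compliant text on both, and the labels or the Trial Materials Manual may already contain it.

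No size can be put on any bias. The in-use time difference is confined to low bolus doses: below about 10.7 U/day, with a range of 4.7 to 21.4 U/day under the assumed priming and parallel-cartridge scenarios, and less often still if part-used product is returned roughly every four weeks. The primary comparison rests on centrally measured HbA1c under common titration recommendations, which limits what an occasional correct guess could do.

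This conclusion assumes that the blinded labels and instructions are the same for both products. The supplied documents neither confirm nor contradict that. No change to the plan follows.

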9.4 Drug accountability and destruction

Drug accountability is the responsibility of the Investigator. The Investigator will perform the drug accountability using the IV/WRS Drug Accountability module.

Subjects are instructed to return all used, partly used and unused trial product at each dispensing visit. See flowchart in section [2](#) for timing of the dispensing visits.

Returned trial product (used/partly used or unused including empty packaging material) can be stored at room temperature and must be stored separately from non-allocated trial product. The Monitor will reconcile the drug accountability using the IV/WRS Drug Accountability module. The Monitor is responsible for ensuring that there is a process for the destruction of used and unused trial products. The destruction of trial products will be recorded on a Destruction Form, which will be signed by the person responsible for destruction. Destruction of products must be documented.

9.5 Auxiliary supplies

9.5.1 Auxiliaries supplied by Novo Nordisk A/S

The following auxiliaries will be supplied by Novo Nordisk A/S:

- NovoPen Echo®
- Direction for use
- BG meters, and ancillary for BG meters
- Needles, the size of the needle will be a maximum of 8 mm
- Standardised liquid meal (for the subgroup only)
- CGM supplies as described in [Appendix B](#) (for the subgroup only)
- Strips for ketone measurement
- A fast-acting glucose preparation (e.g. tablets or powder)

10 Interactive voice/web response system

A trial-specific IV/WRS will be set up which can be accessed at any time via the internet or telephone. Access to the IV/WRS must be restricted to and controlled by authorised persons.

IV/WRS is used for:

- Screening
- Screening failure
- Run-in failure
- Randomisation
- Medication arrival
- Run-in dispensing
- Dispensing
- Treatment discontinuation
- Completion
- Code break
- Drug accountability
- Data change

As the trial is blinded with regards to faster-acting insulin aspart and NovoRapid® it is important that, at all times during the trial, only DUNs allocated by the IV/WRS are dispensed to the Subject.

If a Subject requires additional trial product between dispensing visits, the site must perform an additional dispensing session in IV/WRS.

IV/WRS user manuals will be provided to each trial site.

11 Randomisation procedure and breaking of blinded codes

At randomisation (Visit 14) the Subject will be randomised to either faster-acting insulin aspart or NovoRapid®, both in combination with insulin degludec.

The randomisation will be carried out in a 1:1:1 manner to the three different treatment arms described below using the IV/WRS:

- Meal-time faster-acting insulin aspart and insulin degludec
- Meal-time NovoRapid® and insulin degludec
- Post-meal faster-acting insulin aspart and insulin degludec

The randomisation will be stratified according to age at randomisation (Visit 14):

- $1 \leq \text{age} < 3$
- $3 \leq \text{age} < 6$
- $6 \leq \text{age} < 12$
- $12 \leq \text{age} < 18$

The Investigators must strive to include Subjects in the youngest age groups (age < 6), to enable investigation of the efficacy and safety of faster-acting insulin aspart in these age groups. It will be attempted to include at least 20 Subjects below 6 years of age in each treatment arm.

The bolus insulin treatment is double blinded, except for the post-meal faster-acting insulin aspart treatment arm.

11.1 Breaking of blinded codes

The IV/WRS will notify Novo Nordisk (monitor and the Global Safety department) immediately after the code is broken.

The code for a particular Subject may be broken in a medical emergency if knowing the actual treatment would influence the treatment of the Subject. Whenever a code is broken the person breaking the code must print the Code Break Confirmation Notification generated by the IV/WRS, record the reason, and sign and date the document.

When the code is broken, the treatment allocation will be accessible to the Investigator and the Novo Nordisk Global Safety department. If IV/WRS is not accessible at the time of code break the IV/WRS vendor helpdesk should be contacted. The IV/WRS vendor helpdesk is available at all hours. Contact details are listed in Attachment I.

If the code has been broken the Subject must discontinue trial product and a discontinuation of trial product session must be completed in IV/WRS.

12 Adverse events, and technical complaints and pregnancies

